Active substance	Immunoglobulins: respiratory syncytial virus immune globulin intravenous, immunoglobulin G, freeze-dried pepsin-treated human normal immunoglobulin, pH4-treated acidic human normal immunoglobulin, pH4-treated acidic human normal immunoglobulin (for s.c. injection), polyethylene glycol-treated human normal immunoglobulin, freeze-dried pH4-treated human normal immunoglobulin, freeze-dried sulfonated human normal immunoglobulin, freeze-dried polyethylene glycol-treated human normal immunoglobulin, immunoglobulin M human, immunoglobulin A, Rho(D) immune globulin, tetanus immune globulin, varicella-zoster immune globulin, hepatitis B immune globulin, rabies immune globulin human, Immunoglobulin Anti-Rubella, human vaccinia immune globulin, staphylococcus epidermidis immunoserum rabbit, staphylococcus aureus immunoserum, cytomegalovirus immune globulin, diphtheria antitoxin, hepatitis A immunoglobulin (systemic), Immunoglobulin Anti-Tickborne Encephalitis, pertussis immunoglobulin; systemic, measles immunoglobulin; systemic mumps immunoglobulin; systemic, anthrax immune globulin, Bacillus anthracis immunoserum rabbit, Nebacumab, raxibacumab, bezlotoxumab, obiltoxaximab, palivizumab, MOTAVIZUMAB, tixagevimab, ansuvimab, sotrovimab, REGDANVIMAB, casirivimab, nirsevimab, Sipavibart
Medicinal product	Immunoglobulin brands: Flebogamma DIF, Kiovig, Privigen, Octagam, Yimmugo, Ig vena, Intratect, Iqymune, Panzyga/Globiga, Gamunex, Hizentra, Hyqvia, Cuvitru, Cutaquig, Xembify, Gammagard, Nanogam/Optiglobin, Clairyg, Tegeline, Pentaglobin, Keycute/Naxiglo, Gammaplex, Beriglobin, Rhesonativ, Rhophylac
Research question and objectives	
Research question:
 
What are the treatment and patient characteristics of individuals receiving immunoglobulins across European countries?
 
Study objectives:
 
 
1. To estimate the overall and annual prevalence of immunoglobulin use in the general population, overall and stratified by i) type of immunoglobulin, and ii) route of administration. Estimates will be stratified by age and sex.
 
2. To describe the distribution and quarterly trends of prespecified immunoglobulin brands among prevalent immunoglobulin users (if available).
 
3. To estimate the number of immunoglobulin prescriptions, treatment duration, and dose (initial, cumulative) of immunoglobulin use during the study period.
 
4. To characterise patients initiating treatment with prespecified immunoglobulins in terms of i) demographics at index date, ii) indication for use, iii) comorbidities, iv) common infections post-index, and v) antibiotics post-index.
 

Countries of study	France, Germany, United Kingdom
Authors	[name], [contact] [name], [contact]

## LIST OF ABBREVIATIONS

Acronyms/terms	Description
ATC	Anatomical Therapeutic Chemical
CC	Coordinating centre
CDM	Common Data Model
CDW Bordeaux	Clinical Data Warehouse of Bordeaux University Hospital
CPRD GOLD	Clinical Practice Research Datalink GOLD
DA	Disease Analyzer
DARWIN EU®	Data Analysis and Real-World Interrogation Network
DDD	Defined daily doses
DOI	Declaration of Interests
DQD	Data Quality Dashboard
DRE	Digital Research Environment
DTZ	Data Transfer Zone
EHR	Electronic Health Records
EMA	European Medicines Agency
ENCePP	European Network of Centres for Pharmacoepidemiology and Pharmacovigilance
EU	European Union
EUPAS	EU Post-Authorisation Studies Register
GDPR	General Data Protection Regulation
GP	General Practitioner
ICD	International Classification of Diseases
IG	Immunoglobulin
IP	Inpatient
IRB	Institutional Review Board
OHDSI	Observational Health Data Sciences and Informatics
OMOP	Observational Medical Outcomes Partnership
OP	Outpatient
RxNorm	Medical prescription normalised
SNOMED	Systemised Nomenclature of Medicine
WHO	World Health Organisation

## 1. TITLE

DARWIN EU® - Assessment of immunoglobulin use in clinical practice

### 3. ABSTRACT

#### Title

DARWIN EU® - Assessment of immunoglobulin use in clinical practice

#### Rationale and background

Immunoglobulins can be routinely administered as replacement therapy in immunodeficient patients or are used as immunomodulating doses to treat various immune-related and inflammatory diseases. The global demand of immunoglobulins increases every year, resulting in intermittent shortages that could affect individuals with conditions that have limited alternative treatments. Prolonged low levels of certain immunoglobulins can increase the risk of certain infections and replenishment of these immunoglobulins can reduce this risk. This study aims to generate real-world evidence on the treatment and characteristics of individuals receiving immunoglobulins.

#### Research question and objectives

##### Research question

What are the treatment and patient characteristics of individuals receiving immunoglobulins across European countries?

##### Objectives

The specific objectives of this study are:

1. To estimate the overall and annual prevalence of immunoglobulin use in the general population, overall and stratified by i) type of immunoglobulin, and ii) route of administration. Estimates will be stratified by age and sex.
2. To describe the distribution and quarterly trends of prespecified immunoglobulin brands among prevalent immunoglobulin users (if available).
3. To estimate the number of immunoglobulin prescriptions, treatment duration, and dose (initial, cumulative) of immunoglobulin use during the study period.
4. To characterise patients initiating treatment of prespecified immunoglobulins in terms of i) demographics at index date, ii) indication for use, iii) comorbidities, iv) common infections post-index, and v) antibiotics post-index.

#### Methods

##### Study design

A descriptive retrospective cohort study will be conducted to estimate the prevalence of individuals with a recorded immunoglobulin prescription in the general population, to estimate the prevalence of individuals with a record of a prespecified immunoglobulin brand among prevalent immunoglobulin users, and to characterise individuals receiving immunoglobulin treatment, using routinely collected health data from 3 data sources from 3 countries across Europe for the period from 2017 to 2024.

##### Population

###### *Objective 1*

The study population will include all individuals who are present in the data source during the study period between 01/01/2017 and 31/12/2024.

### *Objective 2*

The study population will include all individuals who have a drug prescription or dispensing record of immunoglobulin and are present in the data source during the study period between 01/01/2017 and 31/12/2024.

### *Objectives 3–4*

For primary care data sources, the study population will include all individuals who initiate immunoglobulin treatment with prespecified immunoglobulin brands and are present in the data source during the study period. Individuals are required to have 180 days data visibility prior to study inclusion and should not have a record of an immunoglobulin prescription in the 180 days prior to study inclusion. To ensure sufficient follow-up time, only individuals who initiated immunoglobulin treatment at least 180 days before the end of the available data will be included.

For hospital care data settings, the study population will include all individuals who have an immunoglobulin record and are present in the data source during the study. Individuals are not required to have prior data availability, and no washout period will be applied prior to study inclusion. To ensure sufficient follow-up time, only individuals who initiated immunoglobulin treatment at least 180 days before the end of the available data will be included.

### Variables

*Drug of interest:* immunoglobulins

*Relevant covariates and other variables:* demographics, prespecified indication for use, comorbidities, prespecified common infections, and prespecified antibiotics

### Data sources

1. France: Clinical Data Warehouse of Bordeaux University Hospital (CDW Bordeaux)
2. Germany: IQVIA Disease Analyzer Germany (IQVIA DA Germany)
3. United Kingdom: Clinical Practice Research Datalink GOLD (CPRD GOLD)

### Study size

No sample size has been calculated, as this is an exploratory study which will not test a specific hypothesis. Based on a preliminary feasibility assessment, the expected number of person counts for immunoglobulins in the data sources included in this study range from 10,900 (CDW Bordeaux) to 73,600 (CPRD GOLD).

### Statistical analysis

#### *Objective 1*

The prevalence of individuals with a recorded immunoglobulin prescription (expressed as the proportion of individuals with any immunoglobulin prescription in the study population) will be stratified by immunoglobulin ingredient, and route of administration, presented overall and per calendar year. Estimates will be stratified by age and sex. These analyses will be conducted using the *IncidencePrevalence* R packages based on OMOP CDM mapped data.

#### *Objective 2*

The quarterly prevalence of individuals with a prespecified immunoglobulin brands prescription will be estimated (expressed as the proportion of individuals prescribed a specific immunoglobulin brand among prevalent immunoglobulin users). These analyses will be conducted using the *IncidencePrevalence* R packages based on OMOP CDM mapped data.

### Objective 3

The number of immunoglobulin prescriptions, treatment duration, and initial and cumulative dose of the index drug will be provided per prespecified immunoglobulin brand as minimum, q25 median, q75, and maximum. This analysis will be conducted using the *DrugUtilisation* R package based on OMOP CDM mapped data.

### Objective 4

Characteristics of individuals initiating treatment with prespecified immunoglobulin brands during the study period will be described for each prespecified immunoglobulin brand by means of large-scale characterisation and prespecified patient-level characteristics. Categorical variables will be summarised as counts and proportions, while continuous variables will be reported as minimum, q25, median, q75, and maximum. Demographic characteristics, including age and sex, will be assessed at the date of immunoglobulin initiation (index date). Characterisation of prespecified indications for use will be assessed any time prior to 7 days after the index date, 30 days prior to 7 days after the index date, and 7 days prior to 7 days after the index date. Large-scale characterisation of comorbidities prior to immunoglobulin treatment will be assessed within 30 days prior to the index date, within 1 year prior to the index date, and any time prior to the index date. Characterisation of prespecified common infections and prespecified antibiotics treatment among prespecified immunoglobulin brand initiators will be assessed up to 30 days post-index and up to 365 days post-index. These analyses will be conducted using the *CohortCharacteristics* and *DrugUtilisation* R packages based on OMOP CDM mapped data.

A minimum cell count of 5 will be used when reporting results, with any smaller count reported as "<5" and zero counts as "0".

## 4. AMENDMENTS AND UPDATES

None.

## 5. MILESTONES

Study milestones and deliverables	Planned dates*
Final Study Protocol	19 January 2026
Creation of Analytical code	December 2025/January 2026
Execution of Analytical Code on the data	January 2026
Draft Study Report	30 January 2026
Final Study Report	To be confirmed by EMA

\*Planned dates are dependent on obtaining approvals from the internal review boards of the data sources.

## 6. RATIONALE AND BACKGROUND

Immunoglobulins are purified products from plasma of human donors. They can be routinely administered as replacement therapy in immunodeficient patients or are used as immunomodulating doses to treat various immune-related and inflammatory diseases.[1, 2] Immunoglobulins are not only used for authorised indications, such as primary immunodeficiency disorders and Kawasaki disease, but also for unauthorised (off-label) indications.[3] Prolonged low levels of certain immunoglobulins can increase the risk of certain infections and replenishment of these immunoglobulins can reduce this risk.[4] The global demand of immunoglobulins increases every year, resulting in intermittent shortages that could affect individuals with conditions that have limited alternative treatments.[1, 3] This study aims to generate real-world evidence on the treatment and characteristics of individuals receiving immunoglobulins.

## 7. RESEARCH QUESTION AND OBJECTIVES

### Research questions

What are the treatment and patient characteristics of individuals receiving immunoglobulins across European countries?

### Research objectives

The specific objectives of this study are:

1. To estimate the overall and annual prevalence of immunoglobulin use in the general population, overall and stratified by i) type of immunoglobulin, and ii) route of administration. Estimates will be stratified by age and sex.
2. To describe the distribution and quarterly trends of prespecified immunoglobulin brands among prevalent immunoglobulin users (if available).
3. To estimate the number of immunoglobulin prescriptions, treatment duration, and dose (initial, cumulative) of immunoglobulin use during the study period.
4. To characterise patients initiating treatment with prespecified immunoglobulins in terms of i) demographics at index date, ii) indication for use, iii) comorbidities, iv) common infections post-index, and v) antibiotics post-index.

## 8. RESEARCH METHODS

### 8.1. Study design

A cohort study will be conducted using routinely collected health data from 3 data sources from 3 countries across Europe and in 3 EU member states. The study will comprise of:

- A population-level drug utilisation study which will be conducted to address *objectives 1* and *2*, assessing the prevalence of individuals with a recorded immunoglobulin prescription, stratified by type of immunoglobulin and route of administration, among the general population (**Figure 1a**) and the prevalence of prespecified immunoglobulin brands among individuals with an immunoglobulin prescription (**Figure 1b**).
- A patient-level drug utilisation study which will be conducted to address *objectives 3* and *4*, assessing treatment characteristics and clinical characteristics of individuals initiating treatment with prespecified immunoglobulin brands, including dose, treatment duration, number of prescriptions, and indication for use, comorbidities, and common infections and antibiotics prescribed (**Figure 2**).

[figure not shown]

Figure 1a. Graphical depiction of the study design *objective 1*.

- Stratification by sex or age group (i) 1 to 18 years, ii) 19 to 65 years, and iii) >65 years and older) will be done at cohort entry date.
- Earliest of: 1) loss to follow-up, 2) death, 3) end of observation period (the latest available data), or 4) study end date 31/12/2024.

[figure not shown]

Figure 1b. Graphical depiction of the study design *objective 2*.

- Earliest of: 1) loss to follow-up, 2) death, 3) end of observation period (the latest available data), or 4) study end date 31/12/2024.

[figure not shown]

Figure 2. Graphical depiction of the study design *objectives 3–4*.

- a. Criterion only applies for primary care data sources (IQVIA DA Germany and CPRD GOLD)
- b. Indication for use include the following prespecified indication groups 1) primary immunodeficiency syndrome, 2) secondary immunodeficiencies, 3) neurology, 4) haematology, 5) infectious diseases, 6) solid organ transplantation, 7) internal medicine, 8) hepatology, and 9) other indications. Detailed information can be found in [Section 8.6.3](#).
- c. Overview of prespecified infections and antibiotics can be found in [Section 8.6.3](#).
- d. Earliest of: 1) loss to follow-up, 2) death, 3) end of observation period (the latest available data), or 4) study end date 31/12/2024

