#### *Objectives 3–4*

##### Inclusion criteria

- Present in the data source during the period of 01/01/2017 to 31/12/2024.
- Minimum 180 days of available history before index data. This criterion does not apply for hospital data source CDW Bordeaux.
- First drug prescription or dispensing record of prespecified immunoglobulin brand during the study period.
- No prior immunoglobulin exposure in the 180 days prior to the index date. This criterion does not apply for hospital data source CDW Bordeaux.

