### 8.6.3. Covariates, including confounders, effect modifiers, and other variables

The variables for *objective 1* are as follows:

- Calendar period
  - Year
- Route of administration:
  - Intravenous
  - Subcutaneous
  - Intramuscular
  - Other
  - Missing
- Age groups, defined at cohort entry date:
  - Overall population
  - 1 to 18 years
  - 19 to 65 years
  - >65 years and older
- Sex, defined at cohort entry date:
  - Overall
  - Male
  - Female

The variables for *objective 2* are as follows:

- Calendar period
  - Quarter of year
- Prespecified brands, including (if available):
  - Flebogamma DIF
  - Kiovig
  - Privigen
  - Octagam (5% and 10%)
  - Yimmugo
  - Ig vena
  - Intratect
  - Iqymune
  - Panzyga/Globiga
  - Gamunex
  - Hizentra
  - Hyqvia
  - Cuvitru
  - Cutaquig
  - Xembify
  - Gammagard
  - Nanogam/Optiglobin
  - Clairyg
  - Tegeline
  - Pentaglobin
  - Keycute/Naxiglo
  - Gammaplex
  - Beriglobin
  - Rhesonativ
  - Rhophylac

The variables for characterisation of immunoglobulin users (*objective 4*) are as follows:

- Demographics, at index date:
  - Sex: Female/male
  - Age
  - Age group: 1 to 18 years, 19 to 65 years, >65 years and older

- Indication for use: Prespecified conditions will be used as proxies to assess the indication for immunoglobulin use, including both authorised and non-authorised indications. The assessment windows will be any time prior to 7 days after the index date [-inf, +7], 30 days prior to 7 days after the index date [-30, +7], and 7 days prior to 7 days after the index date [-7, +7].
  - Primary immunodeficiency syndrome, including:
    - Primary immunodeficiency syndromes
  - Secondary immunodeficiencies, including:
    - Secondary immunodeficiencies
  - Neurology, including:
    - Guillain Barré syndrome (GBS)
    - Chronic inflammatory demyelinating polyradiculoneuropathy (CIDP)
    - Multifocal motor neuropathy (MMN)
    - Myasthenia gravis
    - Stiff person syndrome
    - Lambert-Eaton myasthenia syndrome
  - Haematology, including:
    - Immune thrombocytopenia (ITP)
    - Acquired von Willebrand disease
    - Foetal Neonatal Alloimmune Thrombocytopenia (FNAIT)
  - Infectious diseases, including:
    - Measles
  - Solid organ transplantation, including:
    - Transplantation
  - Internal medicine, including:
    - Kawasaki's disease
    - Inflammatory myopathy
    - (Juvenile) dermatopolymyositis
    - ANCA vasculitis (replacement therapy)
    - Systemic lupus erythematosus (SLE)

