Primary immunodeficiency syndrome	Transient hypogammaglobulinemia of infancy	4230184	No	SNOMED
Secondary immunodeficiencies	Secondary immune deficiency disorder	4140977	No	SNOMED
Secondary immunodeficiencies	Adult-onset immunodeficiency	42536602	No	SNOMED
Transplantation	Solid organ transplant to recipient	4208341	No	SNOMED
Transplantation	Transplantation of bone marrow	4028623	No	SNOMED
Systemic infections	Sepsis caused by Gram negative bacteria	40493038	No	SNOMED
Systemic infections	Bacteraemia	132736	No	SNOMED
Bacterial infections	Bacterial infectious disease	432545	No	SNOMED
Central nervous system infections	Meningitis	435785	No	SNOMED
Fungal infections	Opportunistic mycosis	432248	No	SNOMED
Fungal infections	Invasive fungal infection	36717290	No	SNOMED
Gastrointestinal & intra-abdominal infections	Peritonitis	196152	No	SNOMED
Gastrointestinal & intra-abdominal infections	Gastrointestinal infection	37396146	No	SNOMED
Gastrointestinal & intra-abdominal infections	Acute diarrhea	4261727	No	SNOMED
Respiratory & ear, nose, throat, ocular infections	Sinusitis	4283893	No	SNOMED
Respiratory & ear, nose, throat, ocular infections	Respiratory tract infection	4170143	No	SNOMED
Respiratory & ear, nose, throat, ocular infections	Otitis	4183452	No	SNOMED
Respiratory & ear, nose, throat, ocular infections	Conjunctivitis	379019	No	SNOMED
Respiratory & ear, nose, throat, ocular infections	Bronchitis	256451	No	SNOMED
Urinary infections	Urinary tract infectious disease	81902	No	SNOMED
Viral infections	Herpesvirus infection	435463	No	SNOMED
Viral infections	Disease caused by Picornaviridae	4022207	No	SNOMED

\* = Prespecified indications of use classified as 'Other indications' will be assessed overall and separately for each indication, where available, as specified in [section 8.6.3](#).

List of medicines concepts definition is provided in the table below:

Table S3. Preliminary list of immunoglobulin and antibiotic ingredient definitions.

Substance Name	Concept name	Class	ATC code	Ingredient Concept ID	Include descendants
respiratory syncytial virus immune globulin intravenous	respiratory syncytial virus immune globulin intravenous	Immunoglobulins	J06B	19013765	Yes
immunoglobulin G	immunoglobulin G	Immunoglobulins	J06BA	19117912	Yes
freeze-dried pepsin-treated human normal immunoglobulin	freeze-dried pepsin-treated human normal immunoglobulin	Immunoglobulins	J06BA	35197905	Yes

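### All age bands start at 1 year while no criterion excludes infants, so children under 1 count in the totals but in no age stratum

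*Protocol*

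**What the plan says.** Four places in the Protocol define the age bands, and all start at 1 year:

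- Section 8.1, Figure 1a notes (objective 1): "Stratification by sex or age group (i) 1 to 18 years, ii) 19 to 65 years, and iii) >65 years and older".
- Section 8.6.3, objective 1 variables: the same three bands under "Age groups, defined at cohort entry date", listed beside an unstratified group, "Overall population".
- Section 8.6.3, objective 4 variables: "Age group: 1 to 18 years, 19 to 65 years, >65 years and older".
- Section 8.8.4, Table 4 shell: three age-group rows, again from 1 year, each with N (%).

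Section 8.3 contains no age limit. Objective 1 requires only presence in the data source during 2017 to 2024 and has no exclusions. Objectives 3–4 add history, first-use and follow-up conditions but none on age. One of these, for IQVIA DA Germany and CPRD GOLD only, is "Minimum 180 days of available history before index data"; CDW Bordeaux is exempt.

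The prespecified indications include conditions named for early life: foetal/neonatal alloimmune thrombocytopenia (FNAIT) in section 8.6.3, with a neonatal concept in Table S2, and "Transient hypogammaglobulinemia of infancy" within the primary immunodeficiency set of Table S2.

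**The concern.** The eligibility criteria and the age bands do not describe the same population. Either infants are in the study and the age stratification omits them, or they were meant to be out and the eligibility criteria omit that limit. The protocol does not say which, and gives no reason for starting at 1 year.

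Objective 1 promises estimates by age, and section 8.8.4 promises a figure by ingredient and age group. For any ingredient with some use in the first year of life, that figure would leave those users out without saying so. In Table 4 the same gap would appear as age-group percentages that do not reach 100%, with no note to explain why. A protocol that looks for neonatal and infancy indications should be able to show the age group in which they arise.

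**Working it through.** No sample size, power or alpha is stated, so there is no figure of the plan to reproduce. The checks are of coverage and simple arithmetic.

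**1. Coverage of the bands.** Whole-year ages 0 to 110 were tested against 1–18, 19–65 and >65 (66 and over). Age 0 is the only one in no band. With a <1 year band, or a first band of 0–18, every age falls in exactly one.

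**2. Effect on sums.** Let N be all persons in an analysis and N0 those banded at age 0.

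- N = N0 + N(1–18) + N(19–65) + N(>65)
- Sum of the three reported bands = N − N0
- Sum of Table 4 age percentages = 100 × (1 − N0/N), assuming the denominator is the number of subjects

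N0 is not in the documents. For illustration only, assumed infant shares of 1%, 5% and 20% give age percentages summing to 99%, 95% and 80%. In objective 1 the same identity applies separately to users (numerator) and persons observed (denominator). Overall prevalence then includes a group that appears in none of the age-specific estimates.

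**3. Where infants still count.** Overall, sex, ingredient and route estimates do not depend on the age bands, so infants remain in all of them. Table 4 also reports age as a median with quartiles and as a range, and infants contribute to both.

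**4. Age fixed at entry.** Sections 8.1 and 8.6.3 define age group at cohort entry for objective 1. The study period runs from 01/01/2017 to 31/12/2024, which is 2,921 days; 2,921 / 365.25 = 8.0 years. Read literally, a child who enters before the first birthday is never banded while observed, for at most that long.

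**5. The 180-day rule (objectives 3–4, primary care only).** A child aged d days has at most d days of history, so d must be at least 180.

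- 180 / 30.4375 = 5.9 months
- 180 / 365.25 = 0.49 of the first year of life

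Initiators under about 6 months therefore cannot enter in IQVIA DA Germany or CPRD GOLD. In IQVIA DA Germany observation starts at the first recorded event (Section 9), so the effective minimum age can be higher. In CDW Bordeaux the rule is waived: infants can enter, but Table 4 has no age row for them.

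**The case against.** The other side has real substance. Nothing in the overall results is wrong: infants are counted there, ingredient-level prevalence is complete, and Table 4's age summary includes them. The study is descriptive and tests no hypothesis. Where all three band counts are reported, a careful reader could recover infants by subtraction, although suppression of counts below 5 can prevent this and nothing tells the reader to try. This limits the harm but leaves the mismatch between bands and eligibility.

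Several stronger readings are tempting, and the documents do not support them.

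- *Infants are missing from the results altogether.* They are missing only from the age strata.
- *Infants are the main recipients of several listed products.* The ingredient list does include "palivizumab, MOTAVIZUMAB, tixagevimab, ansuvimab, sotrovimab, REGDANVIMAB, casirivimab, nirsevimab, Sipavibart" and an RSV immune globulin, but the protocol nowhere gives users' ages. Relevance has to rest on its own neonatal and infancy indications.
- *The 180-day rule removes users of the RSV products.* These appear in the ingredient list (Table S3, objective 1) but not in the brand list (Table S4) that defines objectives 3–4, so the rule does not touch them.
- *In 2024, ages 1 to 7 are lost from the 1–18 band, 7/18 = 39%.* This counts single years of age, not children, and assumes continuous observation from infancy. IQVIA DA Germany and CDW Bordeaux observe people only between first and last contact, with median first observation periods of 116 and 247 days (Annex II). Children first seen at age 1 or later are banded normally. The range is also off: children born in 2016 can be age 0 on 01/01/2017 and reach 8 in 2024.
- *Neonatal indications will be near zero in two of the three sources because of the 180-day rule.* This was not computed and cannot be from the protocol. Older infants qualify, and the any-time-prior window picks up earlier diagnoses in later initiators.

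The 180-day rule is also a reasoned choice. Section 9 explains it and warns that it may favour chronic conditions. Only the mention of infants is missing.

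**Conclusion.** The point holds as a mismatch between eligibility and age bands. Followed as written, the plan yields age-stratified results for objective 1, and age-group rows for objective 4, that leave out children under 1 without saying so and do not add up to the total. This rests on the text alone: no age limit in 8.3, and bands from 1 year in all four places.

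The size cannot be stated as a count or share of users, because the documents give no age distribution. What can be stated is that one whole-year age is uncovered, and that a child entering at age 0 could remain unbanded for at most 8.0 years. The latter assumes that age at cohort entry is applied literally and the child is observed throughout.

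The 180-day effect is secondary. It is confined to objectives 3–4, to the listed brands and to the two primary care sources. It calls for disclosure rather than a change of rule.

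**What to change.** **Main change.** Add a <1 year band in section 8.1 (Figure 1a notes), in both age lists of section 8.6.3 and in the Table 4 shell. Alternatively, make the first band 0 to 18 and show <1 separately. Either also gives a band to children who enter before their first birthday. If infants were meant to be outside the study, state an age limit of 1 year in section 8.3 instead, so that the totals match the bands.

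**Secondary change.** Add a sentence to Section 9 saying that the 180-day history requirement excludes initiators of the listed brands under about 6 months of age in IQVIA DA Germany and CPRD GOLD. Leave the eligibility rule as it is. Counting observation from birth as sufficient history would be hard to apply where observation starts at the first recorded event, as in IQVIA DA Germany.

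**Cost.** One age-band parameter, one more row or line in the outputs, and one sentence. Some <1 year cells will be suppressed as <5. The change should be made before the analytical code is executed, which section 5 schedules for January 2026.
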